13.2.2. Secondary Outcome Measures

The secondary outcomes are a combination of binary data, continuous data and count data.

Binary outcomes:

The secondary outcomes that are binary (e.g. VTE related death) will be analysed using the same methods described for the co-primary outcomes (see Section 13.2.1).

Continuous outcomes:

For those secondary outcomes that are continuous (e.g. EQ-5D-5L), linear regression methods will be used for analysis. Results will be presented as adjusted mean difference. If data is found to be not normally distributed, then transformation of the data to get it into a normally distributed form (e.g. log-transformation) will be conducted prior to any analysis.

Count data outcomes:

For those secondary outcomes that are count data types (e.g. Hospitalisations, Unscheduled visits), Poisson regression model will be used for analysis. Time will be used as an offset in the model. Results will be presented as an adjusted incidence rate ratio.

Reclassification rates from thoracic radiologist review:

Reclassification rates for all recruited patients will be calculated with 95% binomial exact confidence intervals for (a) no SSPE and (b) PE requiring anticoagulation as the risks arising from misclassification are different in these patients' populations with implications for implementation as NHS practice does not currently include radiological review. These rates will be analysed without any adjustment. These reclassification rates by trial arm will be included in the table of baseline characteristics. Variation between centres will be described anonymously as understanding centre contribution to reclassification rates may be relevant to intervention implementation. Radiological review of the SSPE diagnosis by the acute reporting radiologist is required as a safety check to ensure randomised patients receive appropriate treatment, that is, anticoagulation of patients with no SSPE randomised to anticoagulation can be halted and anticoagulation of patients with PE which requires it can be initiated.

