8.2.2. Secondary Outcomes

There are a number of secondary outcome measures from the time of randomisation including:

- Recurrent VTE or clinically relevant bleeding at 6 months and 12 months (as assessed through HES records)
- Net clinical benefit composite of clinically relevant bleeding and recurrent VTE at 3 and 6 months.
- New diagnosis of pulmonary hypertension or right ventricular dysfunction within 12 months of SSPE, defined from HES clinical coding and supported where possible by additional radiological data and echocardiograms undertaken in tertiary pulmonary hypertension centres.
- All-cause mortality at 3, 6 and 12 months
- VTE related mortality at 3, 6 and 12 months
- Cardiovascular mortality at 3, 6 and 12 months defined as cardiac deaths (e.g., cardiogenic shock, fatal arrhythmia, cardiac rupture) and vascular deaths (e.g., VTE-related, fatal stroke, ruptured aortic aneurysm, aortic dissection).
- Reclassification rate from thoracic radiologist review

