13. STATISTICAL CONSIDERATIONS

13.1.Sample Size

The trial is powered on the superiority for bleeding events and non-inferiority for recurrent VTE.

Superiority for bleeding events:

With 90% power and two-sided alpha=0.05, to detect a decrease in major bleeding or CRNMB from 7% (based on a meta-analysis of DOAC RCTs)² in the anticoagulation group to 3% in the no anticoagulation group using a two-sample proportions test, 1244 patients (622 per group) are required.

Non-inferiority for recurrent VTE:

We also aim to detect whether no anticoagulation is non-inferior to treatment with anticoagulation regarding VTE recurrence. With 90% power, and a one sided alpha=0.025, a VTE recurrence rate of 2% with anticoagulation (also based on the DOAC RCT meta-analysis)² and a non-inferiority margin of 2.5%, 1,320 patients would be needed. Taking the largest of the two sample sizes computed (i.e. sample size for non-inferiority), allowing for 10% attrition, a total of 1466 patients (733 per arm) would be needed. Sample size calculations were performed using Stata 13.

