13.2. Analysis of Outcome Measures

A separate Statistical Analysis Plan will be produced and will provide a more comprehensive description of the planned statistical analyses. A brief outline of these analyses is given below.

The primary comparison groups will be composed of those treated without anticoagulation versus those treated with anticoagulation. All analyses will be based on the intention to treat principle as well as the per-protocol, with per-protocol set being patients with confirmed SSPE based on CTPA review.

For all outcome measures, appropriate summary statistics will be presented by group (e.g. proportions/percentages, mean/standard deviation or median/interquartile range). Intervention effects will be adjusted for the minimisation variables listed in section 6.2 and baseline scores where possible. 95% confidence intervals (CI) and p-values will be presented for all outcomes. No adjustment for multiple comparisons will be made.

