13.2.1. Primary Outcome Measure

The multiple (joint) primary outcomes are both binary outcomes (i.e. yes/no) and will be analysed using a generalised linear model (with binomial distribution and log link), adjusting for minimisation variables listed in Section 6.2. Treatment effects will be expressed as adjusted risk ratios with 95% CIs. If the model does not converge, then a Poisson regression models with log link and with robust variance estimation will be used (28). We will also present the adjusted risk difference alongside the adjusted risk ratio and so to estimate the adjusted risk difference, a generalised linear model (with binomial distribution and identity link) will be fitted adjusting for minimisation variables listed in Section 6.2.

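### Section 13.2.2 sends VTE-related death to log-link models that break down when one arm has no deaths: usually no usable interval, and at times a spurious p<0.001 from the fallback

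*Protocol*

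**What the plan says.** Section 8.2.2 lists "VTE related mortality at 3, 6 and 12 months" among the secondary outcomes. Section 13.2.2 fixes the analysis and uses this very outcome as its example: "The secondary outcomes that are binary (e.g. VTE related death) will be analysed using the same methods described for the co-primary outcomes".

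Those methods are in Section 13.2.1. The first choice is a "generalised linear model (with binomial distribution and log link), adjusting for minimisation variables". Then: "If the model does not converge, then a Poisson regression models with log link and with robust variance estimation will be used". For the risk difference, "a generalised linear model (with binomial distribution and identity link) will be fitted", with no alternative named if it fails. Section 13.2 adds that "95% confidence intervals (CI) and p-values will be presented for all outcomes".

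The minimisation variables include the randomising site. Section 13.2.1 points to Section 6.2 for them, but the list is in Section 6.4.1. Section 3.2 plans about 50 sites. Section 13 has no rule for outcomes with zero or very few events.

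**The concern.** VTE-related death is one part of a composite that is itself planned at 2%, so an arm without a single such death is a realistic outcome. The log risk ratio then has no finite estimate. The first-choice model cannot give a meaningful interval, and the fallback gives a confident but false one, because its robust variance stays small while the coefficient runs off towards infinity.

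Readers will look at VTE-related death when they judge whether withholding anticoagulation is safe. Under the stated rule the same data, for example 0 v 1 death, can be reported with p near 1 or with p far below 0.001, depending on a convergence flag in the software. A pre-specified method should not leave that open.

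**Working it through.** **Inputs.** From Section 13.1: "a VTE recurrence rate of 2% with anticoagulation", a margin of 2.5 percentage points, and "With 90% power, and a one sided alpha=0.025". Allocation is 1:1 (Section 6.4.1). No rate of VTE-related death is given, so a range is assumed in step 4.

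**1. The plan's own sample size.** n per arm = (1.960 + 1.282)² × 2 × 0.02 × 0.98 / 0.025² = 10.507 × 62.72 = 659.0, rounded up to 660, or 1,320 in total. This agrees with Section 13.1, so 660 evaluable patients per arm is used below. The sample size is sound and is not at issue.

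**2. Why the fallback fails with an empty arm.** Take n per arm with 0 and k events, unadjusted. In the arm with events, the sandwich variance of the log risk is k(1 − k/n)/k² = 1/k − 1/n. In the empty arm every residual shrinks with the fitted risk, so its contribution is at most nε²/(nε)² = 1/n, where ε is the fitted risk. The total is about 1/k, so SE ≈ 1/√k. The coefficient meanwhile grows until the software's tolerance stops it. Fits at 660 per arm:

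| Events | Robust SE | p, robust Poisson (statsmodels) | p, robust Poisson (R) | Fisher p |
|---|---|---|---|---|
| 0 v 1 | 1.00 | 2e-92 | 5e-71 | 1.00 |
| 0 v 2 | 0.71 | 9e-183 | 1e-135 | 0.50 |
| 0 v 3 | 0.58 | 2e-300 | 3e-212 | 0.25 |

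For 0 v 1 the log risk ratio was 20.4 in size in statsmodels and 17.8 in R, with SE 1.00 in both. The exact p depends on tolerance. It stayed below 1e-28 in every adjusted run without site.

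**3. What the first-choice model gives.** For 0 v 1, the log-binomial log risk ratio was about 17 to 20 in size, with SE about 3,700 to 12,700 and p 0.996 to 0.999. With SE 12,670 the 95% limits lie 1.96 × 12,670 ≈ 24,800 either side on the log scale, which carries no information. As a control, 1 v 3 events gives a risk ratio of 3 and p=0.34 from both log-link models. The fault needs an empty arm.

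**4. How often one arm is empty.** Planned VTE events per arm are 0.02 × 660 = 13.2. If 5% to 10% are fatal (an assumption), the expected deaths per arm are m = 0.66 to 1.32. With equal true risk, the chance that exactly one arm is empty is 2e^(−m)(1 − e^(−m)):

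- m = 0.66: 2 × 0.517 × 0.483 = 50%
- m = 1.32: 2 × 0.267 × 0.733 = 39%
- m = 2: 2 × 0.135 × 0.865 = 23%
- m = 3: 2 × 0.050 × 0.950 = 9%
- m = 5: 2 × 0.0067 × 0.9933 = 1.3%

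**5. How often the fallback is reached.** Covariate prevalences here are assumed.

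- Without site: with an empty arm, the log-binomial was flagged converged in 99 of 100 adjusted fits. In simulated datasets with any event, it was non-convergent in 0 of 164 in one set and 1 of 247 in another.
- With 50 sites: it was non-convergent in 9 of 99 simulated datasets with events in one set, in 14% to 27% in another, and in 12 of 20 datasets built with an empty arm.

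**6. False positives under the complete rule, with 50 sites.** One set of small simulations gave about 2% to 8% of trials. Another gave 1/80, 4/80 and 1/80 (1.3%, 5.0% and 1.3%) at 0.66, 1.32 and 3 expected deaths per arm.

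**The case against.** The strongest reply is that Section 13.2 calls itself a brief outline and defers detail to a statistical analysis plan, where a sparse-event rule would normally sit. That would answer a complaint about missing detail. It does not answer this one: the protocol already fixes the model, the fallback and the p-value for a named rare outcome, and an analysis plan that only elaborates the text would inherit the fault.

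A second reply is that percentages by group will be shown, so nobody would believe a risk ratio of hundreds of millions beside 0 v 1. That limits the harm, but leaves the choice of replacement until the deaths are known. Nor does the risk difference rescue the plan. Unadjusted, it is usable (1/660 = 0.15 percentage points, p=0.32 for 0 v 1). The adjusted identity-link model that the plan specifies converged in none of 100 fits, even without site.

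Three stronger readings are tempting and are not supported:

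- A reader might infer a false-positive rate of 39% to 50%. That is the chance of an empty arm. It would be the error rate only if the fallback were always used, and the plan uses it only after non-convergence.
- A reader might infer that false significance arises whatever the adjustment. Without site, the first-choice model is nearly always flagged as converged, and the rule then gives p near 1 with an unusable interval.
- A reader might extend the point to all-cause and cardiovascular mortality. No rate is given for either, and the trial admits patients over 70 and some with a history of cancer, so an empty arm is not shown to be likely there.

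It also stands that the death rate is assumed. Section 8.2.1 counts unexplained deaths as VTE-related when PE or DVT cannot be ruled out, and deaths accumulate to 12 months. Both make an empty arm less likely.

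**Conclusion.** The point holds for VTE-related death. If one arm has no such deaths, the prescribed analysis usually yields no interpretable risk ratio or interval. Where the log-binomial is flagged non-convergent, it can report p<0.001 for a single death. The first result follows directly from an empty arm. The second depends mainly on including site, and on the software.

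The size rests on the assumed death rate: an empty arm in 39% to 50% of trials at 0.66 to 1.32 expected deaths per arm, and about 1% at 5. Whole-rule false significance was a few per cent in small simulations. Because non-convergence varied so much between runs, no single error rate should be claimed. The co-primary VTE composite, with about 13 events planned per arm, and the sample size are unaffected. The change is worth making before any deaths are analysed.

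**What to change.** Add to Section 13.2.2, and carry into the statistical analysis plan: for any binary secondary outcome with no events in one arm, or with fewer than a stated total number of events (for example 10), the Section 13.2.1 models are not used. Report instead the counts and percentages by arm, an unadjusted risk difference with an exact or score interval, and Fisher's exact p-value. A Firth-penalised model is an acceptable alternative if named in advance.

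The cost is a sentence or two of text. These outcomes lose covariate adjustment, and the exact test is conservative. With so few events, adjustment would add little that could be trusted.

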13.2.3. Subgroup Analyses

Subgroup analyses will be limited to the same variables used in the minimisation algorithm excluding centre (see section 6.2). Tests for statistical heterogeneity (e.g. by including the treatment group by subgroup interaction parameter in the statistical model) will be performed alongside the effect estimate within subgroups. The results of subgroup analyses will be treated with caution and will be used for the purposes of hypothesis generation only.

13.2.4. Missing Data and Sensitivity Analyses

Every attempt will be made to collect full follow-up data on all study participants; it is thus anticipated that missing data will be minimal. Participants with missing primary outcome data will not be included in the primary analysis in the first instance. This presents a risk of bias, and sensitivity analyses will be undertaken to assess the possible impact of the risk. In brief, this will include worst-case assumption and/or multiple imputation (if deemed appropriate). Full details will be included in the Statistical Analysis Plan.

13.3.Planned Interim Analysis

Interim analyses of safety and efficacy for presentation to the independent DMC will take place during the study. The committee will meet prior to study commencement to agree the manner and timing of such analyses but this is likely to include the analysis of the primary and major secondary outcomes and full assessment of safety (SAEs) at least at annual intervals. Criteria for stopping or modifying the study based on this information will be ratified by the DMC. Details of the agreed plan will be written into the Statistical Analysis Plan. Further details of DMC arrangements are given in section 14.5.

13.4.Planned Final Analyses

The primary analysis for the study will occur once all participants have completed the 12 week assessment and corresponding outcome data has been entered onto the study database and validated as being ready for analysis. This analysis will include data items up to and including the 12 week assessment and no further. Longer term data from further time-points (i.e. 24 and 52 weeks) will be analysed separately once participants have completed the corresponding assessments.

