3. TRIAL DESIGN AND SETTING

3.1.Trial Design

STOP-APE is an investigator led, multicentre, prospective, randomised controlled, open-label, pragmatic clinical trial with central, blinded, independent adjudication committee (CIAC) endpoint assessment over 3 months for efficacy of withholding anticoagulation for ISSPE. The trial is designed to test the superiority for bleeding events and non-inferiority for recurrent VTE.

Participants will be randomised to either the control arm: full dose anticoagulant treatment as standard care, or the intervention arm: withholding anticoagulation. The choice of anticoagulant will be determined by the responsible treating clinician as part of the standard of care. Pre-randomisation empirical anticoagulation treatment will be allowed for up to 7 days immediately prior to randomisation.

The joint (multiple) primary outcomes of recurrent VTE and clinically relevant bleeding will be established from the trial site clinical notes and electronic health records, patient trial follow-ups and centralised data from hospital episode statistics (HES). The local research team will conduct a safety telephone follow up at 4 weeks, with a permitted window of 1 week either side. Trial follow-ups at 12 and 24 weeks will be performed by the local research team via telephone to complete case report forms and questionnaires. A window of \pm 2 weeks will be permitted for follow-ups.

A 12-month internal pilot will assess feasibility and acceptability with safety of randomisation based on acute reporting radiologists' diagnoses, assessed as part of a nested CTPA study. Note: The nested CTPA study will not stop after the 12-month internal pilot phase and so will be conducted for the full duration of the trial.

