8.2.1. Multiple (joint) Primary Outcomes

Composite of recurrent VTE (nonfatal) and/or VTE related death (primary safety outcome) and clinically relevant bleeding, which is a composite of major and clinically relevant non-major bleeding (CRNMB) (primary efficacy outcome) within 3 months post-randomisation.

The following primary outcome definitions will be used by the CIAC:

VTE recurrence

Composite of nonfatal VTE (PE or DVT) recurrence and/or VTE-related death.

PE recurrence

Suspected (new or recurrent) PE with one of the following findings:

- A new intraluminal filling defect in a subsegmental or more proximal pulmonary artery on CTPA or CT thorax with IV contrast
- An extension of an existing subsegmental pulmonary embolism on CTPA or CT thorax with IV contrast
- A new perfusion defect of at least 75% of a segment with a local normal ventilation result (high-probability) on ventilation/perfusion lung scan

 Symptoms suggestive of PE but with an inconclusive CTPA, CT thorax with IV contrast or ventilation/perfusion scan for PE, and with evidence of a new DVT in the lower extremities by compression ultrasound or venography.

DVT recurrence

Suspected (recurrent) DVT with one of the following findings:

- abnormal compression ultrasound
- an intraluminal filling defect on venography (CT/MR/invasive)

Objective testing for PE/DVT recurrence will be encouraged, but in the absence of objective testing, a suspected episode of DVT or PE will be considered as confirmed if it led to a change in anticoagulant treatment at therapeutic dosages.

VTE-related death

- PE based on objective diagnostic testing, autopsy, or
- Death which cannot be attributed to a documented cause and for which PE/DVT cannot be ruled out (unexplained death).

Clinically relevant bleeding

Composite of major bleeding and clinically relevant non major bleeding (CRNMB).

Major bleeding

Is defined by ISTH criteria:

- 1. Fatal bleeding, and/or
- 2. Symptomatic bleeding in a critical area or organ, such as intracranial, intraspinal, intraocular, retroperitoneal, intra-articular or pericardial, or intramuscular with compartment syndrome, and/or
- 3. Bleeding causing a fall in haemoglobin level of 20g L⁻¹ (1.24 mmol L⁻¹) or more, or leading to transfusion of two or more units of whole blood or red cells.

Clinically relevant non-major bleeding (CRNMB)

Is defined by ISTH criteria:

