8.3. Study procedures

The following assessments should be performed at baseline:

- Ethnicity
- Concomitant medications
- Smoking status
- Risk factors for bleeding as defined by ISTH
- VTE symptoms include pleuritic pain, breathlessness, chest pain not pleuritic, syncope, haemoptysis, leg pain (unilateral/bilateral), leg swelling or oedema (unilateral/bilateral)
- VTE recurrence risk factors as defined by ACCP
- Height and weight
- Routine blood tests to include Hb, platelet count, creatinine, eGFR, BNP, NT-proBNP, Troponin T, D dimer
- Modified MRC dyspnoea score
- EQ-5D-5L questionnaire to be completed on paper by patient (only required for patients who will be randomised)

At point of randomisation:

• Provide patient with patient card

The following assessments should be performed at 4 week follow up via telephone call with the patient (a window of one week is permitted) and review of the medical record:

- SAE check
- Survival check
- VTE recurrence
- Anti-coagulation medication check to include cessation of treatment, commencement of treatment and change to type of treatment

The following assessments should be performed at 12 week and 24 week follow up via telephone call with the patient (a window of two weeks is permitted) and review of the medical record:

- SAE check
- Survival check
- VTE recurrence
- Bleeding events major bleeding and clinically relevant non major bleeding
- Anti-coagulation medication check to include cessation of treatment, commencement of treatment and change to type of treatment
- Modified MRC dyspnoea score
- EQ-5D-5L questionnaire
- NHS usage for VTE recurrence and associated symptoms/bleeding events- to include primary care visits, emergency department/ambulatory care/AMU visits, hospitalisations and diagnostic investigations for VTE.

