8.4. Schedule of Assessments

	Screening	Baseline	Telephone Call 1	Telephone Call 2	Telephone Call 3	HES data extraction
			4 weeks (± 1 week)	12 weeks (± 2 weeks)	24 weeks (± 2 weeks)	52 weeks
Consent	X	X				
Eligibility check	Χ	X				
Registration	Χ					
Randomisation		X				
CTPA/CT thorax with contract	Χ					
Medical history	Χ					
Concomitant medications		X				
Ethnicity		X				
Risk factors for bleeding		X				
VTE symptoms and recurrence risk factors		X				
Routine blood tests		Х				
Modified MRC Dyspnoea score		X		X	X	
Pregnancy test	Χ					
Physical exam	Χ					
Vital signs	Χ					
CTPA/CT Thorax upload to PACS		X				
Leg venous ultrasound	Χ					
EQ-5D-5L		X		X	X	
Anticoagulant medication check			X	X	X	
VTE Recurrence			X	X	X	Χ
Bleeding events (major bleeding and clinically relevant non major bleeding)				X	X	Χ
NHS usage for VTE related events/bleeding events				Х	Х	X
SAE check			Х	Х	Х	
Survival check			Х	Х	Х	Х

Notes

- Medical history to include smoking status
- Randomisation provide patient card to patient at point of randomisation
- Bleeding risk factors as defined by ISTH
- Recurrent VTE risk factors as defined by ACCP
- VTE symptoms to include pleuritic pain, breathlessness, chest pain not pleuritic, syncope, haemoptysis, leg pain (unilateral/bilateral), leg swelling or oedema (unilateral/bilateral)
- Routine bloods results to include Hb, platelet count, creatinine, eGFR, BNP, NT-proBNP, Troponin I, Troponin T, D dimer
- Physical examination to include height, weight, pain on lower-limb venous palpation, leg swelling swelling/oedema (unilateral/bilateral), leg erythema (unilateral/bilateral)
- Vital signs to include heart rate, blood pressure, oxygen saturation, respiratory rate
- CTPA/CT thorax upload to PACS to be done immediately following registration of the patient
- Venous ultrasound of both proximal legs using compression ultrasonography from the saphenofemoral junction to the popliteal fossa sampling at three points. If CT/MR venography has already been performed including both proximal legs ultrasonography is not required.
- EQ-5D-5L only required for patients who will be randomised. To be completed on paper by patient at baseline and follow up via telephone call.
- Bleeding events
- Anti-coagulation medication check to include cessation of treatment, commencement of treatment and change to type of treatment

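### The 3-month primary outcomes are analysed on data cut at an assessment that may fall at week 10, and HES, a named source for them, is extracted only at week 52

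*Protocol*

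**What the plan says.** Section 8.2.1 sets the horizon of both joint primary outcomes (recurrent VTE or VTE-related death, and clinically relevant bleeding): "within 3 months post-randomisation".

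Section 8.3 describes how events are collected: "12 week and 24 week follow up via telephone call with the patient (a window of two weeks is permitted"), together with a review of the medical record. Section 8.4 shows the same call as 12 weeks ± 2 weeks, so a valid assessment can take place at any time from week 10 to week 14. The next scheduled contact is at 24 weeks.

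Section 13.4 fixes the timing of the analysis: "The primary analysis for the study will occur once all participants have completed the 12 week assessment" and the data have been validated. It then sets the cut: "This analysis will include data items up to and including the 12 week assessment and no further". The 24- and 52-week data are to be analysed separately.

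Section 3.1 lists the sources for the joint primary outcomes. They are site notes and electronic records, and also "patient trial follow-ups and centralised data from hospital episode statistics (HES"). In section 8.4 the column "HES data extraction" stands at 52 weeks, and section 9.5 also places the NHS digital records at 52 weeks.

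**The concern.** These statements cannot all be followed. Take a participant called at week 10 who has a DVT in week 11, managed as an outpatient. The event meets the definition in section 8.2.1. It would first be collected at the 24-week call or in the 52-week extract, and section 13.4 keeps both out of the primary analysis. Nothing in the protocol requires the call or the record review to reach the 3-month date.

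HES has the same problem. It is named as a source for the primary outcomes but arrives after the analysis that would use it. It matters most for participants who decline trial follow-up but accept follow-up through central NHS bodies, a status that section 8.5 provides for. Section 13.2.4 leaves participants with missing primary outcomes out of the primary analysis in the first instance.

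The stake is the non-inferiority claim. If withholding does cause extra VTE, missing the same fraction of events in both arms shrinks the absolute difference that is judged against a margin of 2.5 percentage points. That makes a false declaration of non-inferiority more likely.

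**Working it through.** **1. Reproduce the plan's figures (section 13.1).** Inputs: VTE rate 2% in both arms, margin 2.5 points, one-sided alpha 0.025, power 90%.

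n per arm = (1.960 + 1.282)² × 2 × 0.02 × 0.98 / 0.025² ≈ 659.03, rounded up to 660, or 1,320 in total, as stated. 1,320 / 0.9 = 1,466.7, against 1,466 stated. The bleeding calculation (7% v 3%) gives 622 per arm, 1,244 in total, as stated. There is no sample-size error here. The margin reproduces the stated number when read as an absolute difference.

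**2. Risk time that can be missed.** A week-10 call leaves 3 of 13 weeks unobserved (23%), or 2 of 12 weeks (17%) if 3 months means 12 weeks. A call at or after the horizon misses nothing.

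**3. Average loss.** The protocol gives no distribution of call times and no hazard shape, so both are assumed. With calls spread evenly over weeks 10–14 and a constant hazard:

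- 13-week horizon: ∫₁₀¹³ (13 − t)/13 × ¼ dt = 4.5/52 = 8.65% of events missed, so f = 0.9135 are seen.
- 12-week horizon: ∫₁₀¹² (12 − t)/12 × ¼ dt = 2/48 = 4.17% missed, so f = 0.9583.

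**4. Non-inferiority error at the margin.** Set the true 3-month risks at 2.0% and 4.5%, multiply each by f, and use 660 per arm with the unpooled normal approximation:

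error = Φ[(0.025 − RD) / SE − 1.960]

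For f = 0.9135 the risks are 1.83% and 4.11%, RD = 2.28 points and SE = 0.93 points. Then (2.50 − 2.28)/0.93 ≈ 0.23, and Φ(0.23 − 1.96) ≈ 0.042.

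| Horizon | Hazard | All calls week 10 | All calls week 12 | Even, weeks 10–14 |
|---|---|---|---|---|
| 13 weeks | constant | 9.9% | 4.0% | 4.2% |
| 13 weeks | early (Weibull shape 0.5) | 5.2% | 3.2% | 3.3% |
| 12 weeks | constant | 6.8% | 2.5% | 3.2% |
| 12 weeks | early (Weibull shape 0.5) | 4.2% | 2.5% | 2.8% |

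The nominal value is 2.5%. These figures assume that no event after the call is captured by another route. With a 12-week horizon, constant hazard, even calls and half of the post-call events captured otherwise (an assumption), f rises to 0.9583 + 0.0208 = 0.979 and the error is again about 2.8%.

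Simulating the Wald interval gives somewhat higher levels throughout: 3.1% with nothing missed, and 5.0% in the 4.2% case. The upward shift is therefore not a product of the approximation.

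**5. Events behind the extreme case.** With all calls at week 10, a 13-week horizon and constant hazard, 660 × 0.02 × 3/13 = 3.0 control events and 660 × 0.045 × 3/13 = 6.9 withheld-arm events are missed.

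**6. Other cases.** With a true rate of 2% in both arms, RD stays at zero. Power rises from 90% to 92% (even calls, 13 weeks) or 96% (all calls at week 10), because fewer events give a smaller SE. For bleeding at 660 per arm, power falls from 91.6% to 82.9% if all calls are at week 10, on the 13-week horizon with constant hazard.

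**The case against.** The best defence is that section 13.4 may mean only that the 3-month report is kept apart from the 24- and 52-week reports. The sentence on separate analysis follows it directly, and section 8.2.1 already defines the outcome by when the event happens. That reading is reasonable, but it is not what the sentence says, and an unseen SAP would have to contradict an explicit limit in the protocol. Exact day counts are ordinary SAP content. A data cut that conflicts with the outcome definition is not.

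The call is also not the only route. SAEs are reported within 24 hours (section 9.4.2), and the patient card asks participants to contact the research team if admitted (section 6.4.3). These may bring in some serious events after an early call. Non-serious events, such as clinically relevant non-major bleeding or a DVT managed as an outpatient, can still escape.

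The protocol also uses 3 months and 12 weeks interchangeably: the EQ-5D-5L is at 12 and 24 weeks in the trial summary and at 3 and 6 months in section 8.2.2.1. On that usage a call at exactly week 12 loses nothing, though earlier calls still do.

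A reader might infer more than the documents support:

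- *Risk time varies by 4 weeks, and a week-14 call adds late events.* Section 8.2.1 excludes events after 3 months, so the gap is at most 3 weeks, or 2 on a 12-week horizon.
- *About a quarter of events are lost.* That needs every call at week 10, a 13-week horizon and a constant hazard.
- *The VTE difference always shrinks toward non-inferiority.* It shrinks only if withholding truly raises VTE. Proportional loss also leaves the risk ratio, the leading effect measure in section 13.2.1, nearly unchanged.

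**Conclusion.** The inconsistency is in the text and should be corrected. Followed literally, the protocol drops in-window events that are first recorded after an early 12-week assessment, and leaves a named source out of the primary analysis.

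The likely size is modest. If the true VTE excess equals the margin and calls are spread evenly over weeks 10–14, the one-sided error is about 2.8–4.2% instead of 2.5%. Where it falls in that range depends on the horizon (12 or 13 weeks), the hazard shape and how much other routes capture. The extreme case is about 10%. The hazard shapes, call-time distributions and capture rate are assumptions, since the protocol gives none of them.

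The direction matters more than the size. For VTE the error moves toward wrongly accepting withholding, whereas the bleeding comparison only loses power.

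**What to change.** 1. State 3 months as one fixed day count (84 or 91 days), use it throughout, and define both primary outcomes by adjudicated event date within it.
2. Require the call, or at least the record review, to take place on or after that day, or to be completed to that day before database lock.
3. Replace the data-cut sentence in section 13.4 with wording such as: *all adjudicated events with onset within the window, from any source, reported before database lock*.
4. Either obtain a HES extract covering the window before lock, or remove HES from the primary-outcome sources in section 3.1.

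The cost is a protocol amendment, and the last participants' primary data arrive a few weeks later. The sample size does not change.
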